10. EXPECTED RESULTS AND NEUROFUNCTIONAL CONSIDERATIONS

10.1 Expected results and their impact in clinical practice

Reducing the loss of visual acuity achieved through stabilization or improvement of optic nerve and retinal function could ultimately lead to a reduction in visual disability secondary to non-arteritic ischaemic neuropathy, with a significant reduction in related costs for the National Health Service.

In NAION patients treated with Citicoline oral solution, one of the following conditions may be observed at the end of follow-up:

- 1) further loss of retinal nerve fibres (OCT with reduced RNFL thickness) and functional reduction of RGCs (PERG reduced in amplitude) and of the Optic nerve (increase in implicit time P100 of VEP);
- 2) further loss of retinal nerve fibres (OCT with reduced RNFL thickness) and functional maintenance of RGC (PERG with unchanged amplitude) and Optic nerve (implicit time P100 of the VEP unchanged);
- 3) maintenance of retinal nerve fibres (OCT with unchanged RNFL thickness) and functional maintenance of RGC (PERG with unchanged amplitude) and Optic nerve (implicit time P100 of the VEP unchanged);
- 4) maintenance of retinal nerve fibres (OCT with unchanged RNFL thickness) and functional increase of RGC (PERG with increased amplitude) and optic nerve (implicit time P100 of VEP reduced);
- 5) improvement of retinal nerve fibres (OCT with increased RNFL thickness) and functional increase of RGC (PERG with increased amplitude) and Optic nerve (implicit time P100 of

VEP reduced);

The results of NAION patients treated with Cisticoline for oral suspension will be compared with those of NAION patients given no treatment to assess the natural evolution of the morpho-functional condition. The following conditions may occur in such patients:

- 1) further loss of retinal nerve fibres (OCT with reduced RNFL thickness) and functional reduction of RGCs (PERG reduced in amplitude) and of the Optic nerve (increase in implicit time P100 of VEP);
- 2) further loss of retinal nerve fibres (OCT with reduced RNFL thickness) and functional maintenance of RGC (PERG with unchanged amplitude) and Optic nerve (implicit time P100 of the VEP unchanged);
- 3) maintenance of retinal nerve fibres (OCT with unchanged RNFL thickness) and functional maintenance of RGC (PERG with unchanged amplitude) and Optic nerve (implicit time P100 of the VEP unchanged);

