1. INTRODUCTION

1.1 Basic Information

The optic nerve is made up of approximately one million nerve fibres that originate from retinal ganglion cells (RGC).

The nerve fibres of the optic nerve can be the site of degeneration processes due to different etiopathogenic mechanisms such as an increase of intraocular pressure (in the case of Glaucoma), ischemic phenomena (in arteritic and non-arteritic ischemic optic neuropathy) infective-inflammatory processes (in Optical Retrobulbar Neuropathy in the case of Multiple Sclerosis).

In particular, non-arteritic Ischemic Optic Neuropathy (NAION) (i.e., not related to autoimmune diseases) is a disease that can have an acute onset with a chronic progression and can affect one eye (monocular) or both (binocular). The disease causes a severe impairment of the visual function understood as decreased visual acuity (VA), loss or reduction of contrast perception, visual field deficits of various kinds in relation to the selective involvement of the optic nerve fibres: arcuate scotoma, blind-central scotomas, upper or lower altitudinal deficit.

From a pathogenetic point of view NAION is most frequently caused by transient hypoperfusion of the head in the optic nerve at level of the posterior ciliary arteries that causes a compartmental syndrome inducing ischemia. In rare cases it can be traced to local embolic phenomena (Hayreh 2011, Kerr et al. 2009).

The neurodegeneration process of the nerve fibres of the optic nerve can be assessed both from a functional point of view using Pattern Electroretinogram recording (PERG) and Visual Evoked Potential (VEP) (Parisi et al. 2008a) and the morphological view by studying the thickness of nerve fibers using optical coherence tomography (OCT) (Kernstock et al. 2014, Akbari et al., 2016, Han et al. 2016).

The literature reports the possibility, in rare cases, of slight spontaneous improvement of the visual function (Hayreh and Zahoruk 1981). However, there is currently no evidence of substantial benefit from specific therapies.

Indeed, currently under debate are the use of intravitreal injections of triamcinolone and anti angiogenics, oral steroid therapy, and intravitreal injection of erythropoietin (Kernstock et al. 2014).

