Patients with NAION were divided randomly into two groups matched by age:

- 1) NAION -T Group: 14 patients were treated with Citicoline. Citicoline was administered orally (Cebrolux - Tubilux, Italy, 1600 mg/day) for 60 days. followed by a suspension period of 4 months for a total of 6 months follow-up
- 2) NAION -NT Group: 12 patients were not treated and the natural evolution of the disease was observed during a follow-up of 6 months.

For this study, randomized for the first six months, it was decided in the sixth month of observation to continue the study as "open" and to continue to treat patients with NAION for a further period of 2 months, followed by 4 months of suspension.

For a more detailed description of the procedures followed and the electrophysiological techniques used, please refer to the original works. (Parisi et al. 2008a, Parisi et al. 2008b)

In analysing the VEP and PERG results, we considered the following parameters: P100 latency time and amplitude N75-P100 (VEP); latency time P50 and amplitude P50-N95 (PERG); difference between latency P100 and P50 (retinal cortical time, SCT).

During the study period the following was observed:

1. VEP: a decrease in the P100 latency time and an increase in amplitude N75-P100 after the two months of treatment; after the suspension period, we found a worsening in electrofunctional responses. At the end of the first follow-up (6 months) the VEP values were significantly different ($P<0.01$) both compared to those of the baseline and compared to those of the control group (NAION -NT).
2. PERG: a decrease in the P50 latency time and an increase in amplitude P50-N95 after the two months of treatment; after the suspension period, we found a worsening in these electrofunctional responses. At the end of the first follow-up (6 months) the PERG values were significantly different ($P<0.01$) both compared to those of the baseline and compared the control group (NAION -NT).
3. SCT: (electrofunctional index of post-retinal nerve conduction derived from the difference between the P100 latency time of the VEP and the P50 latency time of the PERG): a decrease after two months of treatment; after the suspension period we found a worsening of this electrofunctional index. At the end of the follow-up (6 months) the SCT values were significantly different ($P<0.01$) both compared to the baseline and compared the control group (NAION -NT).

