2.2 Secondary objectives

- 1) to study the neurodegenerative processes of the optic nerve in patients suffering from NAION using the correlations between the function of RGC and optic nerve (using the PERG and VEP recording) and the structural modifications of the nerve fibres of the optic nerve (using the OCT evaluation);
- 2) to determine in patients with NAION the potential for neuroenhancement linked to Citicoline administration in oral solution. This will be obtained using the evaluations of the functional condition (PERG/VEP) found after treatment with Citicoline compared to the condition at the time of enrolment. Correlations will also be evaluated between stabilisation and/or function improvement of RGC and the optic nerve with changes in the visual field.
- 3) to study in patients with NAION the potential for neuroprotection linked to Citicoline administration oral solution. This will be evaluated by comparing, at the end of a 9-month follow-up period, the changes of the nerve fibre structure and the optic nerve (via the OCT assessment) found in the group of patients with NAION treated with Citicoline oral solution compared to a group of patients with untreated NAION where the natural progression of neurodegenerative processes will be observed.

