10.2 Neuro-functional considerations

Whatever the result obtained (see points 1-5 of the expected results), the neurodegeneration model used by us (NAION) will provide important information on the potential of neuroenhancement and neuroprotection of Cisticoline, i.e. the therapeutic opportunity to increase the function of RGCs and of the optic nerve in the presence or absence of structural changes. These results may open up new neuropathophysiological considerations regarding degenerative processes that may be present, with different etiologies, in the various diseases that afflict the optic nerve with consequent significant reduction in visual capacity.

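### Section 10.1 lists improvement only for treated patients, and the plan does not require neuroenhancement to be concluded from a treated-versus-control difference

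*Combined protocol and SAP*

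**What the plan says.** Section 10.1 introduces the treated list with "In NAION patients treated with Citicoline oral solution, one of the following conditions may be observed at the end of follow-up" and gives five conditions. Condition 4 is "maintenance of retinal nerve fibres (OCT with unchanged RNFL thickness) and functional increase of RGC (PERG with increased amplitude) and optic nerve", the last shown by a shorter P100 time. Condition 5 adds a gain in RNFL thickness. Treated results are then to be compared with NAION patients "given no treatment to assess the natural evolution of the morpho-functional condition. The following conditions may occur in such patients". Three conditions follow, and they repeat treated conditions 1 to 3.

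Section 10.2 opens: "Whatever the result obtained (see points 1-5 of the expected results), the neurodegeneration model used by us (NAION) will provide important information". Points 4 and 5 exist only in the treated list.

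Three other places bear on how these lists would be read:

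- Section 1.1: "The literature reports the possibility, in rare cases, of slight spontaneous improvement of the visual function".
- Section 2.2, objective 2 (neuroenhancement), rests on "evaluations of the functional condition (PERG/VEP) found after treatment with Citicoline compared to the condition at the time of enrolment". Objective 3 (neuroprotection), by contrast, compares OCT changes at 9 months with the untreated group.
- Section 9.2 assesses differences from baseline at 6 and 9 months in visual acuity, PERG, VEP and OCT by ANOVA for each group at p < 0.05, with Tukey and Games-Howell multiple comparisons. It names no treated-versus-control contrast.

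**The concern.** The untreated arm is there to show what happens without citicoline. A list of possible outcomes that leaves out improvement in that arm conflicts with section 1.1, and it makes any upward change look like a treatment result. On its own this would be loose wording. It gains weight because, for function, nothing else in the plan says that a gain in treated eyes must exceed the gain in control eyes before it is called neuroenhancement. Slight recovery, learning and repeat-test variation can affect both arms, and a before-after reading credits them to the product.

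The lists are also incomplete for their purpose. Section 10.2 wants to learn about increased function with or without structural change, but functional gain with RNFL loss is not listed, nor is any result in which PERG and VEP disagree.

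The visit is unclear as well. The treated list describes the end of follow-up (9 months, three months after the product stops), whereas objective 2 concerns function after treatment. In the pilot study (section 1.2), "after the suspension period, we found a worsening in electrofunctional responses".

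At stake is the interpretation of secondary objective 2 and, to a lesser degree, objective 3. Visual acuity, the primary outcome, is in neither list.

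**Working it through.** **1. Count of the lists in section 10.1**

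| Condition | RNFL | PERG amplitude | VEP P100 | Treated | Control |
|---|---|---|---|---|---|
| 1 | reduced | reduced | longer | yes | yes |
| 2 | reduced | unchanged | unchanged | yes | yes |
| 3 | unchanged | unchanged | unchanged | yes | yes |
| 4 | unchanged | increased | shorter | yes | no |
| 5 | increased | increased | shorter | yes | no |

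Treated: 5 conditions, 2 with improvement. Control: 3 conditions, 0 with improvement.

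**2. Coverage.** Three measures with three states each give 3 × 3 × 3 = 27 patterns. PERG and VEP agree in 3 × 3 = 9 of them and disagree in 27 − 9 = 18. All listed conditions are among the 9, and the treated list has 5 of those. One of the 4 left out is reduced RNFL with increased function.

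**3. Which comparison governs each claim**

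- Neuroenhancement (objective 2): treated PERG/VEP against enrolment. Section 9.2 works for each group. Section 10.1 says the arms will be compared but gives no contrast or rule. Section 10.2 cites the treated list.
- Neuroprotection (objective 3): OCT, treated against untreated. The objective states the between-arm comparison, but section 9.2 does not carry it into a named contrast.

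The gap is therefore mainly in function.

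**4. Size of the possible error.** Let e be the effect of citicoline and c the mean change that would occur in either arm. Then:

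- mean change, treated = e + c
- mean change, control = c
- before-after reading = e + c, so its error is c
- treated minus control = (e + c) − c = e

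Section 9.1 itself takes a before-after gain as the effect for objective 2. PERG amplitude goes from 0.92 to 1.30 microvolts, a gain of 0.38, with SDs 0.29 and 0.25. The pooled SD is √((0.29² + 0.25²)/2) = 0.2707. A two-sided two-sample t-test at 5% with 90% power needs 12 per group, as stated, and 12 × 1.3 = 15.6, rounded up to 16. The share of such a gain not due to citicoline is c/0.38. It runs from none (c = 0) to all of it (c = 0.38, controls gaining as much). The documents give no value of c for PERG or VEP.

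**5. Could measurement noise alone fill conditions 4 and 5?** Assume that change is called beyond two-sided 95% test-retest limits and that eyes and measures are independent. Both conditions need PERG increased (0.025) and P100 shorter (0.025), with RNFL not reduced (0.975). For 16 eyes the expected number is 16 × 0.025 × 0.025 × 0.975 = 0.00975, so the chance of at least one is about 1%. Noise in single eyes is not the mechanism. A shared mean change is.

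**6. Price of the between-arm contrast.** With 16 eyes per arm, independent eyes and a common SD s of change, the standard error of a within-arm mean change is s/√16 = 0.25s. For the difference between arms it is s√(2/16) = 0.354s, larger by a factor √2 = 1.41.

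**The case against.** The strongest reply is that section 10.1 decides nothing. It says what may be seen, sets no cut-off, coding or decision rule, and does not declare other results impossible. Control eyes have the same tests at the same visits, by assessors who do not know the group (section 6), and section 9.2 analyses measured values in both groups. Section 5.1 says that the two groups are there to identify a specific neuroprotective action, 10.1 says the arms will be compared, and the Tukey or Games-Howell comparisons could include the arms. All of this stands, except that comparisons which could include the arms are not a stated contrast.

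A reader might infer that control gains are ruled out, relabelled or lost. The documents do not support that: such gains are recorded and analysed. Nor is 10.1 the only place where arms are compared, since objective 3 does so for OCT.

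A reader might also infer that function is read only at 9 months. It is measured and analysed at 6 and 9 months. Moreover, section 1.2 reports that pilot values after suspension still differed from baseline and from controls (P<0.01).

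Spontaneous recovery may be small here. Section 1.1 calls it rare and slight, and speaks of visual function, not nerve fibre thickness. By its title, the study cited there concerns juvenile diabetics, whereas this trial excludes diabetes and enrols ages 45 to 80, more than 6 months after the episode. This limits the likely size of c. It does not justify leaving c out of the comparison.

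Finally, section 10.2 says that any result will be informative, deterioration included. That is not a claim of benefit. But it ties what will be learned about enhancement and protection to points listed for one arm.

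**Conclusion.** The point holds as a gap in interpretation, not as a bias built into the analysis. The lists are asymmetric (5 against 3 conditions, 2 against 0 with improvement) and conflict with section 1.1 on function. The consequence comes from the combination of three things: objective 2 is judged against enrolment, section 9.2 names no between-arm contrast, and section 10.2 cites only treated points. Together they leave room to call a treated before-after gain neuroenhancement when controls gained as much.

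The possible error equals the mean change in controls. It cannot be put in microvolts or milliseconds from the documents, and it may be small. This rests on the arms being comparable, so that the control change estimates what treated eyes would have done untreated. The exposure is mainly in objective 2. It is weaker for objective 3, which already states a comparison with untreated patients. The primary outcome is not affected by the lists. The change is worth making before the allocation key is opened.

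**What to change.** - **Section 10.1:** use one list of conditions for both arms, as description only. Add functional gain with RNFL loss, and discordant PERG and VEP. State that function for objective 2 is read at the 6-month end-of-treatment visit, with 9 months showing persistence after suspension.
- **Section 10.2:** state that neuroenhancement or neuroprotection is concluded only from the treated-minus-control difference in change from baseline, on the continuous PERG, VEP and OCT values. A change of the same size in both arms is no effect.
- **Sections 2.2 (objective 2) and 9.2:** carry the same rule into both, and name the treated-versus-control contrast in 9.2. Within-arm changes can stay as description.

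This takes wording and the reporting of one contrast for each outcome and visit. It needs no new patients, visits or measurements. The downside is that some treated-arm gains will be offset by control-arm gains, and the between-arm contrast is less precise than the within-arm one (standard error larger by about 1.41 under the assumptions above).

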10.2 Neuro-functional considerations

Whatever the result obtained (see points 1-5 of the expected results), the neurodegeneration model used by us (NAION) will provide important information on the potential of neuroenhancement and neuroprotection of Cisticoline, i.e. the therapeutic opportunity to increase the function of RGCs and of the optic nerve in the presence or absence of structural changes. These results may open up new neuropathophysiological considerations regarding degenerative processes that may be present, with different etiologies, in the various diseases that afflict the optic nerve with consequent significant reduction in visual capacity.

11. DIRECT ACCESS TO ORIGINAL DOCUMENTS

The Investigator/Institution must allow national and foreign Regulatory Authorities and personnel designated by the Independent Ethics Committee direct access, and verification thereof, to all original study documentation, including Informed Consent forms signed by the subjects in the study or their Legally Recognized Representatives and hospital records and/or outpatient records. Those who have direct access to such documentation must take all reasonable precautions to keep the identity of the subjects confidential in compliance with applicable regulatory provisions.

12. QUALITY CONTROL AND ASSURANCE PROCEDURES

12.1 Data collection or Case Report Form

The Case Report Form (CRF) is the hard copy document that is managed by the Investigator **Hospital Department of Visual Neurophysiology and Neuroophthalmology, Bietti-IRCCS Foundation.**

a) Presentation of the CRF

The CRF consists of numbered pages which show in sequence the information required at each visit/assessment of the Patient.

Each individual page of the CRF will be identified by the centre no., Patient initials, Patient screening number, randomization number, trial time and date of the visit.

b) Instructions for compiling the CRF

The CRF must be compiled in Italian, with legible handwriting, in capital letters, using a black ink ballpoint pen. Each individual page must be compiled immediately after the assessments to which it refers, and must be signed by the Responsible Investigator or other qualified person duly authorized, immediately after checking the data transcribed. CRFs should remain available for monitoring and for any audit and/or inspection visits.

If a determination is not available, the corresponding space for its registration must not be left blank, but the wording NA ("Not Available") must be reported; in the case of tests not performed, the corresponding space for registration must not be left blank, but the wording NP ("Not Performed") must be written.

Any correction must be made cancelling the wrong data by crossing it out and entering the correct data near it. Deleted or corrected data should not be erased, masked or corrected, but should remain legible. The correction made must be initialled and dated by the Investigator or by a qualified person designated by him, possibly justifying with a comment, if necessary, the appropriateness of the same.

The copy of each page will remain at the Study Centre as documentation of the clinical case. It will be the responsibility of the Investigator to report on the appropriate form the normal ranges of laboratory parameters provided by the analysis laboratory.

12.2 Clinical Monitoring

The clinical monitoring activities of the study will be entrusted to the **Hospital Department of Visual Neurophysiology and Neurophthalmology, Bietti-IRCCS Foundation,**

Monitoring activities will be conducted in accordance with the Guidelines of the European Union of Good Clinical Practice adopted by Ministerial Decree of 15 July 1997.

12.3 Audits

The Investigator/Institution must allow audits to be carried out as an integral part of the quality assurance system. The Audit is an independent inspection, separate from the monitoring of the study activities and documents to verify whether the relevant study activities have been conducted and whether the data has been recorded, analysed and transmitted in accordance with the protocol, the GCP, SOPs and applicable regulatory provisions.

12.4 Inspections

The Investigator/Institution must allow national and foreign Regulatory Authorities to carry out Inspections.

The Inspection, by one or more Regulatory Authorities, shall consist of the official review of documents, facilities, records and any other resources considered by such authorities as related to the clinical trial.

13. CLINICAL DATA MANAGEMENT

The management of clinical data is entrusted to the

Hospital Department of Visual Neurophysiology and Neurophthalmology, Bietti-IRCCS Foundation.

All statistical analyses will be carried out by personnel of the Bietti Foundation using the SAS software, version 9.2 (SAS Institute, Cary, NC, USA).

14. ETHICS CONSIDERATIONS

All the parties involved in the study agree and will make sure that this trial is conducted in accordance with the ethical principles deriving from the Declaration of Helsinki, Good Clinical Practice (GCP) guidelines and applicable regulatory provisions.

